5.0 Background Drug Information

5.1 Study Medication

5.1.1 Ibrutinib

5.1.2 Formulation/Packaging/Storage/Disposal

Ibrutinib capsules are provided as a hard gelatin capsule containing 140 mg of ibrutinib. All formulation excipients are compendial and are commonly used in oral formulations. Refer to the ibrutinib Investigator's Brochure for a list of excipients.

The ibrutinib capsules will be packaged in opaque high-density polyethylene plastic bottles with labels bearing the appropriate label text as required by governing regulatory agencies. All study drug will be dispensed in child-resistant packaging.

Refer to the pharmacy manual/site investigational product manual for additional guidance on study drug storage, preparation and handling.

Study drug labels will contain information to meet the applicable regulatory requirements.

Any unused or expired drug will be discarded following the MD Anderson Investigational Pharmacy's standard operating procedures.

5.1.3 Dose and Administration

Ibrutinib 560 mg (4 x 140-mg capsules) is administered orally once daily. The capsules are to be taken around the same time each day with 8 ounces (approximately 240 mL) of water. The capsules should be swallowed intact and patients should not attempt to open capsules or dissolve them in water. The use of strong CYP3A inhibitors/inducers, and grapefruit and Seville oranges should be avoided for the duration of the study.

If a dose is not taken at the scheduled time, it can be taken as soon as possible on the same day with a return to the normal schedule the following day. The patient should not take extra capsules to make up the missed dose.

The first dose will be delivered in the clinic on Day 1, after which subsequent dosing is typically on an outpatient basis. Ibrutinib will be dispensed to patients in bottles at each visit. Unused ibrutinib dispensed during previous visits must be returned to the site and drug accountability records updated at each visit. Returned capsules must not be redispatched to anyone.

5.1.4 Overdose

Any dose of study drug in excess of that specified in this protocol is considered to be an overdose. Signs and symptoms of an overdose that meet any Serious Adverse Event criterion must be reported as a Serious Adverse Event in the appropriate time frame and documented as clinical sequelae to an overdose.

There is no specific experience in the management of ibrutinib overdose in patients. No maximum tolerated dose (MTD) was reached in the Phase 1 study in which subjects received up to 12.5 mg/kg/day (1400 mg/day). Healthy subjects were exposed up to single dose of 1680 mg. One healthy subject experienced reversible Grade 4 hepatic enzyme increases (AST and ALT) after a dose of 1680 mg. Subjects who ingested more than the recommended dosage should be closely monitored and given appropriate supportive treatment.

Refer to Section 10.0 for further information regarding AE reporting.

5.1.5 Pharmacokinetics

Distribution: ~10,000 L

Bioavailability: Administration with food increased exposure ~2-fold (compared to overnight fasting)

Protein binding: ~97%

Metabolism: Hepatic via CYP3A (major) and CYP2D6 (minor) to active metabolite PCI-45227

Half-life elimination: 4-6 hours

Time to peak: 1-2 hours

Excretion: Feces (80%; ~1% as unchanged drug); urine (<10%, as metabolites)

6.0 Concurrent Medications/Procedures

6.1 Permitted Concomitant Medications

Supportive medications in accordance with standard practice (such as for emesis, diarrhea, etc.) are permitted. Use of neutrophil growth factors (filgrastim and pegfilgrastim) or red blood cell growth factors (erythropoietin) is permitted per institutional policy. Transfusions may be given in accordance with institutional policy.

Short courses (</=14 days) of steroid treatment for non-cancer related medical reasons (e.g., joint inflammation, asthma exacerbation, rash, antiemetic use and infusion reactions) at doses that do not exceed 100 mg per day of prednisone or equivalent are permitted.

After consultation with the investigator the following may be considered: localized hormonal or bone sparing treatment for non-B-cell malignancies, and localized radiotherapy for medical conditions other than the underlying B-cell malignancies.

Treatment for autoimmune cytopenias are permitted for <14 days at doses that do not exceed 100 mg per day of prednisone or equivalent.

As stated above, patients treated on this protocol may require supportive care treatment (concomitant medications). These medications are considered standard of care and have no scientific contribution to the protocol; therefore no data will be captured on various medications needed or their side effects.

6.2 Medications to be Used with Caution

6.2.1 CYP3A- Inhibitors/Inducers

Ibrutinib is metabolized primarily by CYP3A. Avoid co-administration with strong CYP3A4 or moderate CYP3A inhibitors and consider alternative agents with less CYP3A inhibition.

- If a strong CYP3A inhibitor (eg, ketoconazole, indinavir, nelfinavir, ritonavir, saquinavir, clarithromycin, telithromycin, itraconazole, nefazadone, or cobicistat) must be used, reduce ibrutinib dose to 140 mg or withhold treatment for the duration of inhibitor use. Subjects should be monitored for signs of ibrutinib toxicity.
- If a moderate CYP3A inhibitor (eg, voriconazole, erythromycin, amprenavir, aprepitant, atazanavir, ciprofloxacin, crizotinib, darunavir/ritonavir, diltiazem, fluconazole, fosamprenavir, imatinib, verapamil, amiodarone, or dronedarone) must be used, reduce ibrutinib to 140 mg (for 840 mg/day dose, reduce to 280 mg) for the duration of the inhibitor use. Avoid grapefruit and Seville oranges during ibrutinib/placebo treatment, as these contain moderate inhibitors of CYP3A (see Section 5.1.3)
- No dose adjustment is required in combination with mild inhibitors.

Avoid concomitant use of strong CYP3A inducers (eg, carbamazepine, rifampin, phenytoin, and St. John's Wort). Consider alternative agents with less CYP3A induction.

A list of common CYP3A inhibitors and inducers is provided in Appendix 3. A comprehensive list of inhibitors, inducers, and substrates may be found at <http://medicine.iupui.edu/clinpharm/ddis/main-table/>. This website is continually revised and should be checked frequently for updates.

For the most comprehensive effect of CYP3A inhibitors or inducers on ibrutinib exposure, please refer to the current version of the IB.

6.2.2 Drugs That May Have Their Plasma Concentrations Altered by Ibrutinib

In vitro studies indicated that ibrutinib is not a substrate of P-glycoprotein (P-gp), but is a mild inhibitor (with an IC₅₀ of 2.15 µg/mL). Ibrutinib is not expected to have systemic drug-drug interactions with P-gp substrates. However, it cannot be excluded that ibrutinib could inhibit intestinal P-gp after a therapeutic dose. There is no clinical data available; therefore, to avoid a potential interaction in the GI tract, narrow therapeutic range P-gp substrates such as digoxin, should be taken at least 6 hours before or after ibrutinib.

6.2.3 QT Prolonging Agents

Any medications known to cause QT prolongation should be used with caution; periodic ECG and electrolyte monitoring should be considered.

6.2.4 Antiplatelet Agents and Anticoagulants

Warfarin or vitamin K antagonists should not be administered concomitantly with ibrutinib. Supplements such as fish oil and vitamin E preparations should be avoided. Use ibrutinib with caution in subjects requiring other anticoagulants or medications that inhibit platelet function. Subjects with congenital bleeding diathesis have not been studied. Ibrutinib should be held at least 3 to 7 days pre- and post-surgery depending upon the type of surgery and the risk of bleeding (see Section 6.4).

Subjects requiring the initiation of therapeutic anticoagulation therapy (eg, atrial fibrillation), consider the risks and benefits of continuing ibrutinib treatment. If therapeutic anticoagulation is clinically indicated, treatment with ibrutinib should be held and not be restarted until the subject is clinically stable and has no signs of bleeding. Subjects should be observed closely for signs and symptoms of bleeding. No dose reduction is required when study drug is restarted.

6.3 Prohibited Concomitant Medications

Any chemotherapy, anticancer immunotherapy, experimental therapy, or radiotherapy are prohibited while the subject is receiving ibrutinib treatment.

Corticosteroids for the treatment of the underlying disease is prohibited. Corticosteroids for the treatment of non-cancer related reasons for longer than 14 days and/or at doses > 100mg of prednisone or its equivalent are prohibited.

6.4 Guidelines for Ibrutinib Management with Surgeries or Procedure

Ibrutinib may increase risk of bleeding with invasive procedures or surgery. The following guidance should be applied to the use of ibrutinib in the perioperative period for patients who require surgical intervention or an invasive procedure while receiving ibrutinib:

6.4.1 Minor Surgical Procedures

For minor procedures (such as a central line placement, needle biopsy, thoracentesis, or paracentesis) ibrutinib should be held for at least 3 days prior to the procedure and should not be restarted for at least 3 days after the procedure. For bone marrow biopsies that are performed while the subject is on ibrutinib, it is not necessary to hold ibrutinib for these procedures.

6.4.2 Major Surgical Procedures

For any surgery or invasive procedure requiring sutures or staples for closure, ibrutinib should be held at least 7 days prior to the intervention and should be held at least 7 days after the procedure and restarted at the discretion of the investigator when the surgical site is reasonably healed without serosanguineous drainage or the need for drainage tubes.

6.4.3 Emergency Procedures

For emergency procedures, ibrutinib should be held after the procedure until the surgical site is reasonably healed, or for at least 7 days after the urgent surgical procedure, whichever is longer.

7.0 Study Evaluations

7.1 Disease monitoring

- 7.1.1 Patients will be assessed at 3, 6, 9, and 12 months after the first dose of ibrutinib, then every 6 months for 3 years. After 3 years, patients will be followed according to MD Anderson's Department of Stem Cell Transplant and Cellular Therapy standard of care guidelines.

Table of Evaluations

Protocol 2014-0096	Within 4 weeks of the 1 st dose	Weekly for the first 4 weeks after 1 st dose	Then every 2 weeks for 4 weeks after 1 st dose	Monthly ¹	1 month (+/-5 days) after 1 st dose	2 months (+/-5 days) after 1 st dose	3 months (+/-5 days) after 1 st dose	6 months (+/-15 days) after 1 st dose	9 months (+/-15 days) after 1 st dose	12 months (+/-15 days) after 1 st dose	Every 6 months (+/-15 days) for 3 years after 1 st dose ⁶	Yearly post-transplant while taking ibritinib
History and physical exam, vital signs, performance status					X	X	X	X	X	X	X	X
CBC, creatinine, liver function tests	X	X	X ¹									
Peripheral blood CD4, CD8, immunodeficiency panel ²					X	X	X	X	X	X	X	X
Immunoglobulin levels					X	X	X	X	X	X	X	X
Bone marrow aspiration/biopsy (unilateral)				X ³	X	X	X	X	X	X		
CT scans (neck, abdomen, pelvis)					X	X	X	X	X	X	X	X
PET ⁴												X
Research Tests (Optional)	X ⁵			X ⁵	X ⁵	X ⁵	X ⁵					

¹ Monthly after 1st study drug dose, if no need for dose reductions or holding of medication. Labs may be checked more often at physician's discretion.

² Only repeat immunodeficiency panel in patients with recurrent infections.

³ No bone marrow aspiration/biopsy at Month 1 after the 1st dose if negative pre-transplant.

⁴ PET only if positive at transplant, and do not repeat after it becomes negative.

⁵ See protocol Section 7.4 for details.

⁶ After 3 years, patients will be followed according to MD Anderson's Department of Stem Cell Transplant and Cellular Therapy standard of care guidelines.

7.1.2 The International Working Group response criteria will be used.

Response	Definition	Nodal Masses	Spleen, Liver	Bone Marrow
CR	Disappearance of all evidence of disease	(a) FDG-avid or PET positive prior to therapy; mass of any size permitted if PET negative (b) Variably FDG-avid or PET negative; regression to normal size on CT	Not palpable, nodules disappeared	Infiltrate cleared on repeat biopsy; if indeterminate by morphology, immunohistochemistry should be negative
PR	Regression of measurable disease and no new sites	> 50% decrease in SPD of up to 6 largest dominant masses; no increase in size of other nodes (a) FDG-avid or PET positive prior to therapy; one or more PET positive at previously involved site (b) Variably FDG-avid or PET negative; regression on CT	> 50% decrease in SPD of nodules (for single nodule in greatest transverse diameter); no increase in size of liver or spleen	Irrelevant if positive prior to therapy; cell type should be specified
SD	Failure to attain CR/PR or PD	(a) FDG-avid or PET positive prior to therapy; PET positive at prior sites of disease and no new sites on CT or PET (b) Variably FDG-avid or PET negative; no change in size of previous lesions on CT		
Relapsed disease or PD	Any new lesion or increase by >50% of previously involved sites from nadir	Appearance of a new lesion(s) >1.5 cm in any axis, >50% increase in SPD of more than one node, or >50% increase in longest diameter of a previously identified node > 1 cm in short axis. Lesions PET positive if FDG-avid lymphoma or PET positive prior to therapy	>50% increase from nadir in the SPD of any previous lesions	New or recurrent involvement

Abbreviations: CR, complete remission; FDG, [18F]fluorodeoxyglucose; PET, positron emission tomography; CT, computed tomography; PR, partial remission; SPD, sum of the product of the diameters; SD, stable disease; PD, progressive disease.

7.2 Safety Monitoring

The following labs may be done at the designated time points by their home physician and the results sent to the MDACC clinical research team. The PI/treating physician will review these labs, determine clinical significance, and sign/date the results. Concomitant medication data will not be collected.

7.2.1 Complete blood counts, creatinine, LFTs as follows:

- Weekly for the first four weeks of therapy, then
- Every 2 weeks for 4 weeks, then
- Monthly thereafter (*If no need for dose reductions or holding of medication*)

7.2.2 Patients may have labs checked more frequently at the discretion of the physician.

7.3 Outside Physician Participation During Treatment

MDACC Physician communication with the outside physician is required prior to the patient returning to the local physician.

This will be documented in the patient record. Protocol-specific treatment decisions must be made by the MDACC physician.

A letter to the local physician outlining the patient's participation in a clinical trial will request local physician agreement to supervise the patient's care (Appendix G.).

Protocol required evaluations outside MDACC will be documented by fax or e-mail. Fax and/or e-mail will be dated and signed by the MDACC physician, indicating that they have reviewed it.

Changes in drug dose and/or schedule must be discussed with and approved by the MDACC physician investigator, or their representative prior to initiation, and will be documented in the patient record.

A copy of the informed consent, protocol abstract, and Table of Assessments (Appendix D.) during treatment will be provided to the local physician.

Documentation to be provided by the local physician will include drug administration records, progress notes, reports of protocol required laboratory and diagnostic studies and documentation of any hospitalizations.

The home physician will be requested to report to the MDACC physician investigator all life threatening events within 24 hours of documented occurrence.

[figure not shown]
Patients will return to MDACC every 3, 6, 9, and 12 months, then every 6 months for 3 years after the first dose of ibrutinib, then yearly as long as they are receiving ibrutinib.

7.4 Optional lab studies

7.4.1 Rationale

Please see Section 2.7.

7.4.2 Tests and Schedule

8.0 Criteria for Removal from the Study

- 8.1 Disease progression.
- 8.2 Intolerable side effects.
- 8.3 Unable to follow study directions.
- 8.4 Withdrawal of consent.
- 8.5 Completion of 3 years on study drug.

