1.2 Secondary objectives

1.2.1 Estimate safety and toxicity, DFS, and overall survival (OS).

1.2.2 Estimate efficacy and DFS at 3, 6, 9, 12 months and every 6 months thereafter for 3 years.

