Patients must complete at least two months of treatment or have toxicity to be included in the rule. Patients who complete at least two months but drop out without experiencing toxicity will be included but not counted as toxicities.

This stopping rule was chosen to assure that the probability of early stopping would be approximately 7% if the true rate of toxicity was no more than 30%. The operating characteristics of this rule are shown below. The stopping boundaries and operating characteristics were calculated in the Department of Biostatistics using the software Multc Lean Desktop v1.2.0.

Table 3. Operating Characteristics for Toxicity Stopping Rule

If the true toxicity rate is...	Early Stopping Probability	Achieved Sample Size 25th, 50th, 75th percentiles		
		30	30	30
0.1	0.0002	30	30	30
0.2	0.0070	30	30	30
0.3	0.0709	30	30	30
0.4	0.3114	21	30	30
0.5	0.6875	9	18	30
0.6	0.9338	6	9	16

Secondary and tertiary objectives

For secondary objectives, we will estimate response, safety, and toxicity at 3, 6, 9, and 12 months after treatment initiation and then every 6 months x 3 years with a 95% confidence interval. We may also estimate specific response types such as humoral and cellular. This data will be used to inform future studies. Kaplan-Meier³⁰ survival curves will be used to estimate overall survival and progression-free survival. We will also assess the rates of organ toxicity. Cox proportional hazards regression analysis will be used to model the association between overall survival and progression-free survival and disease and demographic covariates of interest, including data from the correlative cytokine, immune, and Mir studies.

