10.3.2 Adverse Event Reporting Period

All AEs whether serious or non-serious, will be captured from the first dose of study drug until 30 days following the last dose of study drug and will be collected in MD Anderson's Clinical Oncology Research (CORe) system. We will record the AEs' start date, resolution date, and maximum grade.

Serious adverse events reported after 30 days following the last dose of study drug should also be reported if considered related to study drug. Resolution information after 30 days should be provided.

Progressive disease should NOT be reported as an event term, but instead symptoms/clinical signs of disease progression may be reported. (See Section 10.1.1)

All adverse events, regardless of seriousness, severity, or presumed relationship to study drug, must be recorded using medical terminology in the source document. All records will need to capture the details of the duration and the severity of each episode, the action taken with respect to the study drug, investigator's evaluation of its relationship to the study drug, and the event outcome. Whenever possible, diagnoses should be given when signs and symptoms are due to a common etiology (e.g., cough, runny nose, sneezing, sore throat, and head congestion should be reported as "upper respiratory infection").

All deaths should be reported with the primary cause of death as the AE term, as death is typically the outcome of the event, not the event itself.

If a death occurs within 30 days after the last dose of study drug, the death must be reported as a serious adverse event.

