10.3.4 Other Malignancies

All new malignant tumors including solid tumors, skin malignancies and hematologic malignancies will be reported for the duration of study treatment and during any protocol-specified follow-up periods including post-progression follow-up for overall survival. If observed, enter data in the corresponding eCRF.

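### Section 8.0 removes patients from the study at progression while 10.3.4 assumes survival follow-up after it; reconcile the two and state how OS is censored

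*Combined protocol and SAP*

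**What the plan says.** Section 8.0 gives five criteria for removal from the study. The first is "8.1 Disease progression"; the others are intolerable side effects (8.2), inability to follow directions (8.3), withdrawal of consent (8.4) and finishing three years of drug (8.5). It does not distinguish stopping drug from leaving follow-up. The rule for stopping drug stands separately in Section 4.2: relapse, an adverse event that dose adjustment cannot manage, or three years of treatment.

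Four other places bear on follow-up:

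- Section 7.1.1: "Patients will be assessed at 3, 6, 9, and 12 months after the first dose of ibrutinib", and then six-monthly for 3 years. It adds "After 3 years, patients will be followed according to" the institution's standard-of-care guidelines. It does not say whether visits continue after relapse.
- Section 7.3 makes only the later yearly visits conditional on being on drug.
- Section 10.3.4, on new malignancies, counts "post-progression follow-up for overall survival" among the protocol's follow-up periods.
- Section 10.3.2 makes a death reportable as an SAE "If a death occurs within 30 days after the last dose of study drug"; SAEs after that window "should also be reported if considered related to study drug". Section 10.3.6 says much the same.

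OS is a secondary objective (1.2.1). Section 9.0 says Kaplan-Meier "survival curves will be used to estimate overall survival and progression-free survival", with Cox models for both. It gives no censoring rule for OS. Its drop-out rule concerns the primary endpoint only.

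**The concern.** Sections 8.0 and 10.3.4 point in different directions on what happens to a patient who relapses. Under the first, taken literally, the patient leaves the study; under the second, the patient is still followed for survival. Nothing in the available text sets an interval, method or duration for that follow-up.

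If a site follows 8.1 to the letter, a lymphoma death more than 30 days after the last dose, judged unrelated to drug, has no stated route into the data. Patients who have relapsed have a higher risk of death than those in remission, so dropping them at relapse is informative censoring. Kaplan-Meier then overstates OS, and the Cox analysis rests on the same incomplete deaths. With 30 patients, a few unrecorded deaths move the estimate visibly, and survival data not collected at the time can be hard to recover.

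**Working it through.** **The plan's own figure.** The only stated power figure is 80% for 2-year DFS, 50% against 75%, with N = 30. An exact binomial test rejecting at 21 or more of 30 has an upper-tail error of 0.0214 (0.0428 doubled) and power 0.803, so the figure reproduces. It does not depend on this point. The documents give no OS figure to reproduce.

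**The passages side by side.**

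- For removal ending follow-up: the title of Section 8.0, and the fact that 4.2 already holds the drug-stopping rule, so Section 8.0 can be read as going further.
- For removal meaning off drug only: 8.1, 8.2 and 8.5 mirror the reasons in 4.2; 7.1.1 plans follow-up after 3 years although 8.5 removes patients who complete 3 years of drug; 10.3.4 names OS follow-up after progression.

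The second reading is the more coherent, but no sentence states it.

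**Size if 8.1 is applied literally.** From Section 9.0: 2-year DFS of 75% or 50%. From 10.3.2: the 30-day window. Assumed, not in the documents: constant hazards; a share q = 10% or 20% of DFS events are deaths in remission; median survival after relapse of 3, 6, 12 or 24 months; relapse taken as last dose. Later deaths reported as drug-related are not modelled.

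Per month:

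- λ = −ln(DFS)/24; death in remission hd = qλ; relapse hr = λ − hd; death after relapse m = ln 2/median.
- In remission: S0(t) = exp(−λt).
- Alive after relapse: R(t) = hr[exp(−λt) − exp(−mt)]/(m − λ).
- Alive and relapsed within the last w = 30/30.4375 months: Rw(t) = R(t) − exp(−mw)R(t − w), with the second term zero for t < w.
- True OS at 2 years = S0(24) + R(24).
- Kaplan-Meier limit under the 30-day rule = exp(−∫ (hd·S0 + m·Rw)/(S0 + Rw) dt), from 0 to 24.

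Worked case (DFS 75%, q = 20%, median 12 months): λ = 0.01199, hd = 0.00240, hr = 0.00959, m = 0.0578. R(24) = 0.00959 × (0.750 − 0.250)/(0.0578 − 0.01199) = 0.105, so true OS = 0.750 + 0.105 = 0.855. The integral is 0.0695, so Kaplan-Meier gives exp(−0.0695) = 0.933. The gap is 7.8 points.

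All cases, for medians of 3 / 6 / 12 / 24 months:

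| 2-year DFS | q | True 2-year OS | Kaplan-Meier, 30-day rule | Gap, points |
|---|---|---|---|---|
| 75% | 10% | 0.787 / 0.822 / 0.868 / 0.910 | 0.923 / 0.946 / 0.958 / 0.965 | 13.6 / 12.4 / 9.1 / 5.5 |
| 75% | 20% | 0.783 / 0.814 / 0.855 / 0.892 | 0.902 / 0.922 / 0.933 / 0.939 | 12.0 / 10.8 / 7.8 / 4.7 |
| 50% | 10% | 0.564 / 0.631 / 0.725 / 0.812 | 0.826 / 0.876 / 0.904 / 0.919 | 26.2 / 24.4 / 17.9 / 10.7 |
| 50% | 20% | 0.557 / 0.617 / 0.700 / 0.777 | 0.782 / 0.824 / 0.847 / 0.860 | 22.5 / 20.7 / 14.7 / 8.3 |

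For scale, the approximate 95% half-width is 1.96 × √(OS(1 − OS)/30). At DFS 75% and a 3-month median with q = 10%, that is 1.96 × √(0.787 × 0.213/30) = 14.7 points, so the gap of 13.6 is 0.93 of it. At a 24-month median with q = 20%, the half-width is 11.1 and the gap of 4.7 is 0.42 of it.

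**Sensitivity.** With q = 40%, DFS 75% and medians of 3-12 months, the gap falls to 5.5-8.7 points. If every relapsed patient is followed, it is zero.

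**Primary endpoint.** Relapse is already a DFS failure, so 8.1 changes nothing. A patient removed under 8.2 while in remission would be counted as a non-responder if classed as a drop-out. If that patient would have been disease-free at 2 years, the estimated rate falls by 1/30 = 3.3 points.

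**The case against.** A reader might infer that the protocol ends OS follow-up at relapse, apart from deaths caught by the 30-day rule. The documents do not support that. It takes Section 8.0 alone. Section 10.3.4 is current text and names OS follow-up after progression, 7.1.1 does not stop visits at relapse, drug-related SAEs stay reportable after 30 days, and three of the five criteria repeat the drug-stopping reasons. What stands is a conflict between sections and a missing schedule. Even the latter is subject to the appendices, which were not available.

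It is also fair to say that the magnitudes come from outside the documents. Neither survival after relapse nor the share of deaths in remission is given, and the plan names no 2-year OS landmark. The figures are illustrations, not bounds; only the upward direction is secure, given that relapsed patients die faster.

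A reader might further infer that the primary endpoint is compromised. It is not through 8.1. The effect through 8.2 depends on what counts as a drop-out, which Section 9.0 does not define, and counting drop-outs as failures is a stated, conservative choice.

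Finally, censoring at the date last known alive is ordinary practice, and OS here is secondary and descriptive. That limits the weight of the point. But the convention helps only if someone keeps recording whether relapsed patients are alive, and Section 8.0 leaves that in doubt.

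**Conclusion.** The point holds as an unreconciled conflict between Section 8.0 and Sections 7.1.1 and 10.3.4, together with the absence of any OS censoring rule in Section 9.0. It should be corrected, but it is not evidence that OS follow-up is planned to stop at relapse.

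Under literal use of 8.1 and the assumptions above, 2-year OS is overstated by about 5-14 points if 2-year DFS is 75%, and by about 8-26 points if it is 50%. Under the off-drug reading the bias is zero. The sample size and the 80% power are unaffected.

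**What to change.** Reconcile Sections 7.1, 8.0, 9.0 and 10.3.4 with four statements:

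1. The Section 8.0 criteria other than withdrawal of consent end study drug, not follow-up.
2. After relapse or drug stop, vital status is collected through 3 years from first dose, by visit, phone or chart.
3. For patients who stop drug in remission, disease status is taken from assessments already scheduled or done as standard of care, so that stopping drug does not by itself make them drop-outs for 2-year DFS.
4. OS is censored at the date last known alive, not at relapse or drug stop.

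Leave the treatment-stopping rules and the withdrawal-of-consent criterion unchanged. If the off-drug reading was always intended, this is clarification only. The cost is a few sentences and a small amount of extra status tracking in a 30-patient trial; no added scans or marrow examinations are asked for.
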